11.4.2 Secondary Efficacy

[figure not shown]
No secondary efficacy objective is defined for this study.

[figure not shown]
11.4.2.1 Statistical Hypotheses

[figure not shown]
Not applicable.

[figure not shown]
11.4.2.2 Analysis Methods

Not applicable.

[figure not shown]

11.5 Handling of Missing Data

All data obtained in evaluable subjects/eyes will be included in the analysis. No imputation for missing values will be carried out for the efficacy analysis.

11.7 Safety Analysis

The safety endpoints for this study are AEs, biomicroscopy findings, and device deficiencies. Data will be presented by regimen, T/C and T1/T2/C1/C2/C3/C4.

Descriptive summaries (counts and percentages) for ocular and nonocular AEs will be presented by Medical Dictionary for Regulatory Activities (MedDRA) Preferred Terms. In addition to an overall presentation of AEs, relationship to regimen (lens and/or LCS) will be identified. Serious AEs will also be tabulated separately. Individual subject listings will be provided, as necessary.

Additionally, individual subject listings will be provided for AEs that occur after signing informed consent but prior to exposure to study regimens (lens and/or LCS).

Each biomicroscopy parameter will be tabulated by its grade. For each biomicroscopy parameter, counts and percentages of eyes that experience an increase of ≥ 2 grades from baseline (Visit 1) to any subsequent visits will be presented. A supportive listing will be generated which will include all biomicroscopy data from the affected visit for those eyes experiencing the increase of ≥ 2 grades, with the following variables: regimen, Investigator, subject, age, sex, visit, eye, parameter, baseline value, and value at the visit.

[figure not shown]
Frequency counts will be tabulated for each device deficiency category. Additionally, 2 listings will be provided: prior to exposure to study regimens (lens and/or LCS) and treatment-emergent.

No inferential testing will be done for safety analysis.

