2 OVERVIEW OF STUDY PLAN

	Visit 1	Visit 2	Visit 3	Visit 4 / Exit	USV
Procedure/ Assessment	Screening	Day 1- Insertion 1-7 days from Visit 1. No lenses worn on day of the visit	Day 1: 8hrs (± 30 min)	Day 30 (+3 days): 8hrs (± 30 min)/Exit	Unscheduled Visit
Informed Consent	✓				
Demographics	✓				
Medical History	✓				
Concomitant Medications	✓	✓	✓	✓	✓
Inclusion/Exclusion	✓				
Biomicroscopy (Note: conjunctival staining conducted at designated sites only)					
Randomize Eligible Subjects	✓				
Dispense assigned study lenses in a masked manner		✓ ^g			(✓)
Collect lenses for shipping and analyses				✓	(✓)
Exit Form	(✓)	(✓)	(✓)	✓	(✓)
Assess Adverse Events	✓ ^d	✓	✓	✓	✓

(Both observed and reported)					
Assess Device Deficiencies		✓	✓	✓	✓
[REDACTED]					

[REDACTED] ^c Without lenses at baseline to determine eligibility [REDACTED]
[REDACTED] ^d AEs are collected from the time of informed consent. [REDACTED]
[REDACTED] ^e Lenses
also dispensed at Day 15±1 in office for subjects assigned to continue wearing Oasys.

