13	
Remind subjects that spectacles or habitual contact lenses/lens care solutions can continue to be used until the day prior to Visit 2. Habitually worn lenses can be returned or a new pair dispensed. [REDACTED]
 
[REDACTED]
 
[REDACTED]
 
Subjects randomized to habitual SiHy/MPS must have a new bottle of the HMPS, identified during screening, ready for dispensing at Visit 3. This can be accomplished in two ways for the study:
 
 1) The subject purchases a new bottle of the HMPS and brings it to Visit 2. In this case the subject will be reimbursed for their purchase. The unmasked coordinator must confirm the solution purchased was the HMPS identified during screening and that it is not expired. The unmasked coordinator will dispense the purchased HMPS at Visit 3. 2) The site purchases the subject’s HMPS and the unmasked coordinator dispenses to the subject at Visit 3.

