10.2.2 Visit 2 (1-7 Days from Visit 1) – Day 1 Insertion Visit

[figure not shown]
1	Obtain information on any changes in medical health and/or the use of concomitant medications since previous visit.
2	Perform biomicroscopy assessment using slit-lamp examination scales with no conjunctival/corneal staining procedures. Refer to MOP for details.
3	[REDACTED]

4	Unmasked coordinator to dispense randomized study lenses. Record time of lens insertion.
5	
6	
7	
8	
9	
10	Assess and record any AEs that are observed or reported (see Section 12).

11	Record any Device Deficiencies that are observed or reported (see Section 12).
12	

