11.2 Analysis Data Sets

11.2.1 Safety Data Set

Safety analyses will be conducted using the safety analysis set on a treatment-emergent basis. The safety analysis set will include all subjects/eyes exposed to the study lens and/or the study lens care system (LCS) evaluated in this study as a regimen. For treatment-emergent safety analyses, subjects/eyes will be categorized under the actual lens or regimen exposed.

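### The 2-grade biomicroscopy count in Section 11.7 literally includes the Visit 2 examination made before the first study lens, in conflict with the treatment-emergent basis of Section 11.2.1

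*Protocol*

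**What the plan says.** Section 11.7 names Visit 1 as the baseline for biomicroscopy. For each parameter it counts eyes with a rise of at least 2 "grades from baseline (Visit 1) to any subsequent visits will be presented". On layout it says "Data will be presented by regimen, T/C and T1/T2/C1/C2/C3/C4". A supportive listing shows the affected eyes with regimen, visit, baseline value and value at the visit. The same section gives separate listings for adverse events and device deficiencies that precede exposure. It states no such separation for biomicroscopy.

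Section 11.2.1 sets the general rule: "Safety analyses will be conducted using the safety analysis set on a treatment-emergent basis". It adds that eyes are classified by the lens or regimen to which they were actually exposed.

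Section 10.2.2 fixes the order of events at Visit 2. Step 2 reads "Perform biomicroscopy assessment using slit-lamp examination scales with no conjunctival/corneal staining procedures". Step 4 reads "Unmasked coordinator to dispense randomized study lenses. Record time of lens insertion". The visit table in Section 2 says of Visit 2: "No lenses worn on day of the visit". In the 1 to 7 days between the visits, Section 10.2.1 allows spectacles, or else "habitual contact lenses/lens care solutions can continue to be used until the day prior to Visit 2".

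**The concern.** A grade rise seen at step 2 of Visit 2 arose on spectacles or on the subject's own lenses and solution. It cannot be an effect of study lenses dispensed two steps later. Yet it meets the Section 11.7 definition, and the results are shown by regimen. For a subject assigned to AOHG, a change that arose on the habitual lens could then appear in an AOHG column.

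What is at stake is how the biomicroscopy worsening table is read. If programmed from Section 11.7 alone, it would mix pre-exposure with post-exposure changes, while the adverse event and device deficiency outputs beside it keep them apart. The primary cholesterol endpoint is not involved.

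**Working it through.** The protocol gives no expected number of 2-grade rises, so there is no figure to reproduce. The check compares the visit order with the counting window.

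**Visit order**

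| Examination | Source | Exposed to study lens? | In the literal window? |
|---|---|---|---|
| Visit 1 | 10.2.1, step 9 | No | Baseline |
| Visit 2, step 2, no staining | 10.2.2 | No, lenses come at step 4 | Yes |
| Visit 3, about 8 hours later, no staining | 10.2.3 | Yes | Yes |
| Visit 4/Exit | 10.2.4, steps partly redacted | Yes | Yes, if biomicroscopy is done there |

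So one scheduled visit inside the window is examined before exposure. It would be one of three if Visit 4 includes biomicroscopy, which the redacted steps do not let us confirm.

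**Which parameters.** Neither conjunctival nor corneal staining is done at Visit 2, so a Visit 2 staining rise cannot exist. Only the other slit-lamp parameters are affected.

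**Whether removing Visit 2 from the window is enough.** Take an eye with grade g at Visit 1 (illustrative grades):

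| Case | Visit 1 | Visit 2, before insertion | Visit 3 | Literal rule | Visit 2 dropped, Visit 1 kept as baseline | From last pre-exposure grade |
|---|---|---|---|---|---|---|
| A: rise resolves | g | g+2 | g | Counted at Visit 2 | Not counted | Not counted |
| B: rise persists | g | g+2 | g+2 | Counted at Visits 2 and 3 | Counted at Visit 3: (g+2) − g = 2 | Not counted: (g+2) − (g+2) = 0 |
| C: fall, then rise | g | g−1 | g+1 | Not counted: (g+1) − g = 1 | Not counted | Counted: (g+1) − (g−1) = 2 |

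Case B shows that narrowing the window is not sufficient: a rise present before insertion and still there at Visit 3 is counted against Visit 1. Case C shows that the Visit 1 reference can also miss a rise that followed exposure.

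**Weight of one eye.** Planned numbers are 256 subjects, 64 per habitual lens type, allocated 1:1 to AOHG or habitual lenses, with AOHG then split 1:1 by solution (Sections 8 and 9).

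- Each control regimen: 64 × 1/2 = 32 subjects, or 32 × 2 = 64 eyes. One eye is 1/64 = 1.6 percentage points.
- Each test regimen: 256 × 1/2 × 1/2 = 64 subjects, or 128 eyes. One eye is 1/128 = 0.8 percentage points.

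These figures assume that every randomized subject contributes both eyes. They show the leverage of one miscounted eye, not how many there would be.

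**The case against.** The strongest reply is that Section 11.2.1 already governs. If all safety analyses are treatment-emergent and eyes are classified by actual exposure, a change seen before insertion should not count, and Section 11.7 is only loosely worded. This stands in part. A reader might infer from Section 11.7 that pre-exposure changes will be charged to a regimen; the protocol does not support that, because its general rule points the other way. What remains is a conflict. Section 11.7 is the specific rule, names its own baseline and window, and makes the pre-exposure split explicitly for the other two safety endpoints but not for this one. Nor does the general rule say which grade to measure from once Visit 2 is set aside (case B).

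The reply that the effect is slight also stands. Subjects are randomized at Visit 1 and all may keep their habitual products until the day before Visit 2, so such changes should fall equally on the test and control arms. No inferential safety testing is planned. The listing carries the visit, so Visit 2 rises can be traced. Each parameter is also tabulated by grade, and Section 12.2 requires clinically relevant changes to be reported as adverse events.

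Two further inferences are tempting. One is that percentages would be understated because the visit table has "conjunctival staining conducted at designated sites only". Section 11.7 names no denominator and does not say that unexamined eyes enter it; that detail ordinarily belongs in the statistical analysis plan, which is not at hand. The other is to put a number on the eyes miscounted. The protocol gives no rate of 2-grade change on habitual lenses over 1 to 7 days, so any such number would be invented.

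**Conclusion.** The point holds as an unreconciled conflict between the window in Section 11.7 and the treatment-emergent basis in Section 11.2.1. Followed literally, Section 11.7 counts an examination made before exposure. It does not follow that the sponsor will report the data that way.

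It is a minor point. It is confined to non-staining parameters, adds noise rather than bias between the randomized arms, and concerns one descriptive table whose listing lets the affected eyes be found. Its size cannot be derived from the protocol; the only scale available is that one eye moves a control-regimen percentage by about 1.6 points and a test-regimen percentage by about 0.8 points at the planned numbers. The conclusion rests on the stated order of steps at Visit 2, which is explicit, and not on any assumed event rate.

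**What to change.** In Section 11.7:

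- Count 2-grade increases only at examinations after the first study-lens insertion: Visit 3, Visit 4, and unscheduled visits that follow insertion.
- Measure each increase from the last pre-exposure grade: Visit 2 for parameters graded there, Visit 1 for staining parameters. Use the same reference as the baseline value in the supportive listing.
- List increases from Visit 1 already present at Visit 2 before insertion separately as pre-exposure, matching the treatment of adverse events and device deficiencies.

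The cost is a short wording change, a small change to one safety table and its listing, and one additional listing. The Visit 2 grades are already collected, so no visit, procedure or sample size changes.

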11.8 Health Economics

Not applicable.

12 ADVERSE EVENTS

12.1 General Information

An AE is any untoward medical occurrence, unintended disease or injury, or untoward clinical signs (including abnormal laboratory findings) in subjects, users, or other persons, whether or not related to the investigational medical device (test article). Refer to the Glossary of Terms for categories of AEs and SAEs.

Figure 12-1 Categorization of All Adverse Events

[figure not shown]
[figure not shown]

Figure 12-2 **Categorization of All Serious Adverse Events**

12.2 Monitoring for Adverse Events

At each visit, after the subject has had the opportunity to spontaneously mention any problems, the Investigator should inquire about AEs by asking the standard questions:

- “Have you had any health problems since your last study visit?”
- “Have there been any changes in the medicines you take since your last study visit?”

Changes in *biomicroscopy parameters and/or subject questionnaires* evaluated during the study are to be reviewed by the Investigator. Any untoward (unfavorable and unintended) change that is clinically relevant, in the opinion of the Investigator, is to be reported as an AE. These clinically relevant changes will be reported regardless of causality.

12.3 Procedures for Recording and Reporting AEs and SAEs

AEs are collected from the time of informed consent. Any pre-existing medical conditions or signs/symptoms present in a subject prior to the start of the study (ie, before informed consent is signed) are not considered AEs in the study and should be recorded in the Medical History section of the eCRF.

In addition, temporary lens awareness or visual changes during the fitting process are not considered AEs if the Investigator assesses that the symptom(s) can reasonably resolve within the anticipated adaptation period.

For each recorded event, the ADEs and SAEs documentation must include: date of occurrence, severity, treatment (if applicable), outcome, and assessments of the seriousness and causality. In addition, the Investigator must document all device deficiencies observed or reported with test and control articles on the Device Deficiency eCRF. The site must submit all available information on ADEs, SAEs, and device deficiencies to the Study Sponsor immediately as follows:

- All SAEs must be reported immediately (within 24 hours) of the Investigator's or site's awareness.
- ADEs that do not meet seriousness criteria and device deficiencies must be reported within 10 calendar days of the Investigator's or site's awareness.
- A printed copy of the completed *Serious Adverse Event and Adverse Device Effect* and/or *Device Deficiency* eCRF must be included with product returns. Refer to MOP for product return details.
- Additional relevant information after initial reporting must be entered into the eCRF as soon as the data become available.
- Document any changes to concomitant medications on the appropriate eCRFs.
- Document all relevant information from Discharge Summary, Autopsy Report, Certificate of Death etc., if applicable, in narrative section of the Adverse Device Effect (for related AEs) and Serious Adverse Event eCRF.

Note: Should the EDC system become non-operational, the site must complete the appropriate paper *Serious Adverse Event and Adverse Device Effect* and/or *Device Deficiency* Form. The completed form is emailed to the Study Sponsor to [REDACTED] according to the timelines outlined above; however, the reported information must be entered into the EDC system once it becomes operational.

Any AEs and device deficiencies for non-study marketed devices/products will be considered and processed as spontaneous (following the postmarket vigilance procedures) and should be communicated to the device's/product's manufacturer as per local requirements.

Study Sponsor representatives may be contacted for any protocol related question and their contact information is provided in the MOP that accompanies this protocol.

Further, depending upon the nature of the AE or device deficiency being reported, the Study Sponsor may request copies of applicable portions of the subject's medical records. The Investigator must also report all AEs and device deficiencies that could have led to a SADE according to the requirements of regulatory authorities or IRB/IEC.

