1.1 Glossary of Terms for Safety

Adverse Event (AE)	Any untoward medical occurrence, unintended disease or injury, or untoward clinical signs (including abnormal laboratory findings) in subjects, users or other persons, whether or not related to the investigational medical device (test article). Note: For subjects, this definition includes events related to the test article, the control article, or the procedures involved. For users or other persons, this definition is restricted to events related to the test article.
Adverse Device	Adverse event related to the use of an investigational medical device (test article) or control article. Note: This definition

Effect (ADE)	includes adverse events resulting from insufficient or inadequate instructions for use, deployment, implantation, installation, or operation; any malfunction; and use error or intentional misuse of the test article or control article.
Device Deficiency	Inadequacy of a medical device with respect to its identity, quality, durability, reliability, safety, or performance. Note: This definition includes malfunctions, use errors, and inadequate labeling.
Malfunction	Failure of a medical device to meet its performance specifications or otherwise perform as intended. Performance specifications include all claims made in the labeling of the device. The intended performance of the device refers to the intended use for which the device is labeled or marketed.
Product Complaint	Any oral, electronic, or written communication that alleges deficiencies related to the identity (labeling), quality, durability, reliability, safety, effectiveness, or performance of a marketed product, including failure of the product, labeling or packaging to meet specifications, whether or not the product is related to or caused the alleged deficiency. A complaint may allege that an adverse event or medical device malfunction has occurred.
Non-serious Adverse Event	Adverse event that does not meet the criteria for a serious adverse event.

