Serious Adverse Event (SAE)	Adverse event that led to any of the following: 
 • Death. • A serious deterioration in the health of the subject that either resulted in: 
 a) a life-threatening illness or injury. Note: Life-threatening means that the individual was at immediate risk of death from the event as it occurred, ie, it does not include an event which hypothetically might have caused death had it occurred in a more severe form. b) any potentially sight-threatening event or permanent impairment to a body structure or a body function. c) in-patient hospitalization or prolonged hospitalization. Note: Planned hospitalization for a pre-existing condition, without serious deterioration in health, is not considered a serious adverse event. In general, hospitalization signifies that the individual remained at the hospital or emergency

	
ward for observation and/or treatment (usually involving an overnight stay) that would not have been appropriate in the physician's office or an out-patient setting. Complications that occur during hospitalization are adverse events. If a complication prolongs hospitalization or fulfills any other serious criteria, the event is serious. When in doubt as to whether "hospitalization" occurred, the event should be considered serious.
 
 d) a medical or surgical intervention to prevent a) or b). e) any indirect harm as a consequence of incorrect diagnostic test results when used within manufacturer's instructions for use. 
 • Fetal distress, fetal death, or a congenital abnormality or birth defect. 
Refer to Section 12 for additional SAEs.

Serious Adverse Device Effect (SADE)
	
Adverse device effect that has resulted in any of the consequences characteristic of a serious adverse event.

Serious Public Health Threat
	
Any event type which results in imminent risk of death, serious deterioration in state of health, or serious illness that requires prompt remedial action. This would include: Events that are of significant and unexpected nature such that they become alarming as a potential public health hazard, eg, human immunodeficiency virus or Creutzfeldt-Jacob Disease.

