Subjects should be instructed to remove the lenses if any of the above signs or symptoms are noticed. A serious condition such as a corneal ulcer, infection, or iritis may be present, and may progress rapidly. Less serious reactions such as abrasions, infiltrates, and bacterial conjunctivitis must be managed to avoid more serious complications. In addition, the Investigator should advise subjects of possible ocular dryness, increased lens awareness/intolerance, and visual changes with concomitant medications or during pregnancy.

It is important for OFPM and CCP users to follow directions and all labeling instructions for proper use, including use of the lens case. Subjects who are noncompliant and fail to follow the instructions for cleaning, storage, and disinfection of their contact lenses could experience an eye infection or injury. Contact lens wearers unfamiliar with a hydrogen peroxide solution (CCP) could inadvertently use the peroxide solution as a lubricating/rewetting drop or rinse their contact lenses prior to insertion, resulting in chemical burn due to the unneutralized peroxide solution. Additionally, using the wrong lens cup, overfilling the lens cup with peroxide solution or disinfecting the lenses for less than the specified time can result in incomplete neutralization of the peroxide solution. In such cases, adverse ocular effects such as discomfort, burning, stinging, pain, inflammation or irritation as well as chemical burn or irritation to the fingers may occur. These adverse effects are usually temporary, and users should be instructed to immediately flush the eyes or fingers with saline or water should this occur. Overall, the potential risks associated with use of the subject's Habitual SiHy/MPS, AOHG/OFP, and AOHG/CCP are similar when used as indicated.

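### Device deficiencies that could have led to a serious adverse device effect have no sponsor deadline of their own and fall under the general 10-day limit

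*Protocol*

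**What the plan says.** Section 12.3 of the protocol opens its reporting rules with this lead-in: "The site must submit all available information on ADEs, SAEs, and device deficiencies to the Study Sponsor immediately as follows". Two limits follow:

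- For serious events: "All SAEs must be reported immediately (within 24 hours) of the Investigator's or site's awareness".
- For everything else: "ADEs that do not meet seriousness criteria and device deficiencies must be reported within 10 calendar days", counted from site awareness.

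The second limit does not divide deficiencies by what they might have caused. Later in the same section a further duty appears: "The Investigator must also report all AEs and device deficiencies that could have led to a SADE according to the requirements of regulatory authorities", or those of the IRB/IEC. That sentence names no number of days and does not mention the sponsor.

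The glossary (Section 1.1) defines a device deficiency broadly: "This definition includes malfunctions, use errors, and inadequate labeling". Section 9.1 says that each CCP kit holds a re-labelled bottle and the lens cup with the platinum disk that neutralises the peroxide, and that the label carries a misuse warning. Section 9.2 says that the sponsor provides the care solutions for the test lens.

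**The concern.** The protocol itself marks off the deficiencies that could have led to a SADE, yet for sponsor notification it treats them like any other. Such a deficiency is a near miss: nobody has been seriously harmed, so the SAE limit does not apply and the 10-day limit does.

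This matters most for a fault with a common cause. If one site finds a kit without its disk, or a wrong label, the same fault may be present in kits elsewhere. The sponsor supplies those kits and is the party best placed to warn the other sites. A site can follow Section 12.3 to the letter and still not tell the sponsor for 10 days, while subjects elsewhere go on disinfecting and reinserting lenses daily. The missing disk and the wrong label are illustrations; the protocol reports no such fault.

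**Working it through.** **The rules side by side (Section 12.3)**

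| Report | To the sponsor | To authorities or IRB/IEC |
|---|---|---|
| SAE | 24 hours from awareness | not at issue here |
| Non-serious adverse device effect | 10 calendar days | not at issue here |
| Device deficiency, no SADE potential | 10 calendar days | none stated |
| Device deficiency, SADE potential | 10 calendar days (no separate limit) | per their requirements, no days stated |

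The last two rows differ only in the right-hand column. The duty to authorities is an addition to the 10-day rule and does not alter the sponsor deadline.

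**Does another visible provision shorten it?** Section 12.4 lets the sponsor upgrade the seriousness or causality of AEs; it does not mention deficiencies, and nothing can be upgraded before it is received. Section 12.7 asks for new safety information without a time limit. Section 12.3 refers to the Manual of Procedures for product returns and sponsor contacts, not for a faster limit. No visible passage gives a faster route.

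**Size of the permitted delay.** Inputs: limit 10 days (Section 12.3); treatment 30 days, up to 33 (Synopsis).

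- Maximum delay as a share of treatment: 10/30 = 33.3%, or 10/33 = 30.3%.
- Under the existing 24-hour limit it would be 1/30 = 3.3%, or 1/33 = 3.0%.

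**Number of subjects.** Inputs: about 256 randomised and about 8 weeks of enrolment (Section 8); 1:1 to test or habitual lens, then 1:1 to the two test solutions (Section 9).

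- CCP subjects over the trial: 256 × 1/2 × 1/2 = 64.
- Assumption: starts spread evenly over 8 × 7 = 56 days, each subject wearing lenses for 30 days.
- Most on treatment at one moment: 64 × 30/56 = 34.3, about 34.
- On treatment at some time in a 10-day window: a subject counts if the start falls in the 30 days before the window or the 10 days within it. A window opening on the first day of enrolment gives 64 × 10/56 = 11.4. A window in the later part of enrolment gives at most 64 × 40/56 = 45.7. Counting 64 evenly spaced whole subjects gives about 12 and 45.

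So a window opening during enrolment touches roughly 12 to 45 of the 64, depending on when it opens. Subjects entering later would still receive the same product and label.

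**The case against.** The strongest reply is that the protocol already separates this class, since the duty to report it to authorities or the IRB/IEC is stated. That stands in part. A reader might infer that such a deficiency can go unreported; the text does not support that. What is missing is a sponsor limit, not a duty to report.

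Second, 10 days is a ceiling under a lead-in that says reports go immediately. True, but the lead-in hands over to the list that follows, and the list gives the number. The mismatch is a further reason to reconcile the wording.

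Third, real harm escalates: the SAE definition includes any potentially sight-threatening event, so such an event goes to the sponsor within 24 hours. This stands, and it confines the point to near misses.

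Fourth, a reader might take Section 5.2 to name the handling errors as routes to ocular chemical burn. Its wording on these errors is "using the wrong lens cup, overfilling the lens cup with peroxide solution or disinfecting the lenses for less than the specified time can result in"; the stated result is that the peroxide is not fully neutralised. It then lists discomfort, pain, inflammation or irritation of the eye and chemical burn or irritation of the fingers, and calls these effects usually temporary. Ocular chemical burn is tied to using the peroxide as a drop or as a rinse before insertion. A single subject's use error is also not a fault shared by all CCP subjects. The point therefore rests on kit and label faults.

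Fifth, a reader might want a separate fast limit for the glossary's category of public health threats, which is defined there as "Any event type which results in imminent risk of death, serious deterioration in state of health, or serious illness that requires prompt remedial action". Such an event in a subject would largely be an SAE already, so that addition is not needed.

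Sixth, sites are not powerless: they teach correct case use, and the investigator may discontinue subjects or close the site. That covers one site, not the others.

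Last, Figures 12-1 and 12-2, the Manual of Procedures and the eCRF are not available. This limits the point to what Section 12.3 states, but that is the rule a site would follow.

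**Conclusion.** The point holds in limited form. Section 12.3 gives SADE-potential device deficiencies the same 10-calendar-day sponsor limit as all others, although the same section treats them as a distinct class. The maximum permitted delay from site awareness to sponsor is about a third of the treatment period (30% to 33%).

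About 64 subjects receive CCP over the trial. A reader might infer that all of them are exposed during such a delay. With even accrual over 8 weeks, about 34 at most are on treatment at once, and about 12 to 45 are touched by a 10-day window opening during enrolment. These counts rest on the accrual assumption; the reading of the rules does not.

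This is a rule as stated, not a detail left to another document, and it is worth correcting. It does not affect the endpoints or the analysis. The documents do not themselves say which limit this class should have.

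**What to change.** Reconcile the two rules in Section 12.3. State an explicit expedited sponsor limit for device deficiencies that could have led to a SADE, for example by adding them to the existing 24-hour tier. Keep 10 calendar days for non-serious adverse device effects and all other deficiencies. Reword the lead-in so that it does not promise immediate submission for items that have 10 days. Make sure the Device Deficiency eCRF identifies the class, so that the site knows which limit applies; if the form already does, nothing is needed there.

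The cost is a sentence or two in Section 12.3, at most one eCRF item, and a few more expedited reports. Treatment, visits, endpoints and analysis are unchanged.
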